3.4 Additional Efficacy Endpoints

^{*} Endpoints will be evaluated outside of the gated hierarchical testing.

3.5 Safety Endpoints

Safety evaluations include adverse event (AE) monitoring, vital sign measurements, 12-lead electrocardiogram (ECG) collection, laboratory evaluations (hematology and chemistry), neurological assessment (examination to consist of assessment of cranial nerves II through VII), and physical examinations as measures of safety. The safety endpoints are:

- Incidence of AEs (including any abnormality found during neurological assessment and physical examination)
- Change from baseline in vital sign parameters
- Change from baseline in ECG parameters
- Change from baseline in laboratory evaluations (hematology and chemistry)
- Presence of binding and neutralizing antidrug antibodies (see Section 3.6 for more details)

3.6 Immunogenicity Assessment

Blood samples for immunogenicity testing will be collected from all subjects according to the Study Activities Table (Appendix D). Collected samples will be processed to yield serum for detection of binding and neutralizing antibodies to AGN-151586 and may also be used for additional characterization of antibody response to other neurotoxin subtypes.

4 INVESTIGATIONAL PLAN

4.1 Overall Study Design and Plan

This is a 12-week, multicenter, Phase 3 study designed to evaluate the safety and efficacy of AGN-151586 in treating GL. Subjects are adults (≥ 18 years of age) with moderate to severe GL at maximum frown as assessed independently by both the investigator and subject using the FWS. The investigator and subject ratings for GL will be done at the Screening Visit and at the Baseline Day 1 Visit. The investigator and subject ratings must match within a visit but do not have to match between Screening and Baseline Day 1. Each eligible subject may receive up to 2 study treatments with AGN-151586. The time of study treatment administration defines Hour 0 for the treatment period (on Day 1 for double-blind period and on Day 43 for open-label period).

Eligible subjects will be enrolled into the study containing 2 treatment periods:

Double-blind Period: Screening will occur up to 14 days prior to Baseline Day 1. Randomization and treatment will occur on Baseline Day 1 after all other study procedures have been completed. A single treatment of AGN-151586 or placebo will be administered on Baseline Day 1, based on randomization (3:1 ratio of AGN-151586:placebo). Randomization will be stratified by investigator site, toxin use history (for aesthetic purpose), and baseline GL severity at maximum frown. All enrolled subjects will receive treatment on Baseline Day 1 and attend in-clinic site visits to fully characterize the onset of treatment effect. Thereafter, in-clinic site visits will be completed to characterize the peak and duration of effect.

The double-blind period will end on Day 43. The Day 43 visit will occur 42 ± 2 days following the Day 1 visit. The study assessments conducted during the Day 43 visit serve as the final assessment for the double-blind period and as the baseline assessment for the open-label period.

Open-label Period:

For subjects meeting all the retreatment criteria on Day 43, a single open-label treatment with AGN-151586 will be administered on the same day. The subject will then be followed for approximately 6 weeks (through Day 84). The schedule of the follow-up visits in the open-label period is the same as that in the double-blind period. After each study treatment administration, subjects must remain in the clinic for at least 30 minutes for observation of any AEs.

Retreatment is only permitted on the Day 43 visit.

If the subject does not meet the GL severity criterion at Day 43 visit for retreatment, the subject will be followed weekly as per the Activity Schedule (Appendix D) until the FWS grades assessed by both investigator and subject have returned to moderate or severe (investigator and subject grades do not need to match) before being discontinued from the study after completing either the Early Exit or Study Exit Visit. If the subject becomes pregnant, then study drug may not be administered, and the subject can either be discontinued from the study after Early Exit Visit procedures are completed or remain in the study for all safety follow-up assessments. If the subject declines retreatment despite meeting the retreatment criteria at Day 43 visit, the subject may be discontinued from the study after Early Exit Visit procedures are completed.

[figure not shown]
The efficacy measures include investigator FWS, subject FWS, FLO-11, FLSQ, GAC-GL, .

To assess the safety of AGN-151586 for the treatment of GL, the safety measures are collected in the study are AEs, vital sign measurements, ECG, laboratory evaluations (hematology and chemistry), neurological assessment physical examinations, and immunogenicity.

Prior to commencing any assessment, all makeup must be removed and care must be taken so that hair does not obscure the upper face. All assessments must be completed before administration of study treatment.

The schematic of the study is shown in Figure 1. Further details regarding study procedures are located in the Operations Manual (Appendix F).

See Section 5 for information regarding eligibility criteria.

4.2 Discussion of Study Design

Choice of Control Group

A placebo-control group is the gold standard for comparative evaluations of safety and efficacy in clinical trials and will be used for the double-blind period of the study. No control group will be used for the open-label period.

Appropriateness of Measurements

Standard statistical, clinical, and laboratory procedures will be utilized in this study. All efficacy and safety-related measurements in this study are standard for assessing subjects with GL. All clinical and laboratory procedures in this study are standard and generally accepted.

Suitability of Subject Population

The study population will be adult subjects with moderate or severe GL at maximum frown as assessed by both the investigator and subject using the FWS. Eligibility criteria will be assessed at Screening Visit and Baseline Day 1 Visit to ensure subject safety.

Selection of Doses in the Study

[figure not shown]
In the previous Phase 2b Study 2034-201-008, a clinical dose response was observed, demonstrating that the proportion of responders (i.e., subjects having ≥ 2-grade improvement from baseline as assessed by investigator through Day 7) increased with increasing AGN-151586 dose. The responder rate was approximately 95% for the cohort dosed with related TEAEs was similar between the placebo group (18.0%) compared with the AGN-151586 group (20.9%). There were no safety trends or patterns identified with increasing the dose of AGN-151586. Overall, AGN-151586 had a favorable safety profile and AGN-151586 showed the most robust benefit and thus, AGN-151586 was selected for the Phase 3 pivotal studies.

The dose selected is expected to be efficacious with an acceptable safety profile.

5 STUDY ACTIVITIES

5.1 Eligibility Criteria

Subjects must meet all of the following criteria in order to be included in the study. Anything other than a positive response to the questions below will result in exclusion from study participation. Subjects who do not meet the eligibility criteria for participation in this study (screen failures) may be allowed to be rescreened. Rescreening of subjects must only occur after discussion with the sponsor. Rescreening can only occur once for any given potential subject; however, if the original screen failure was due to ineligible FWS grade(s), the subject will not be permitted to rescreen.

Disease/Condition Activity

[figure not shown]
Ø 6. Subjects must have moderate or severe GL at maximum frown as assessed by both the investigator and subject using the FWS at Screening and Baseline Day 1 Visit.

Subject History

- 7. Subjects must not have uncontrolled systemic disease.
- 8. Subjects must not have received treatment with any botulinum neurotoxin of any serotype for aesthetic treatment within the last 6 months prior to Baseline Day 1 and for therapeutic treatment within the last 12 months
- 9. Subjects do not present with or have a history of any medical condition that may place the subject at increased risk following exposure to AGN-151586 or interfere with the study evaluation.
- 10. Subjects must not have a diagnosis of myasthenia gravis, Lambert-Eaton syndrome, amyotrophic lateral sclerosis, or any other significant disease that might interfere with neuromuscular function.
- 11. Subjects must not have a history of facial nerve palsy.
- 12. Subjects must not have infection or dermatological condition at the treatment injection sites.
- 13. Subjects must not have marked facial asymmetry, dermatochalasis, deep dermal scarring, excessively thick sebaceous skin, excessively photodamaged skin, or the inability to substantially lessen facial lines even by physically spreading them apart.
- 14. Subjects must not have any eyebrow or eyelid ptosis at screening or Baseline Day 1 visit as determined by the investigator.
- 18. Subjects must not have tattoos, jewelry, or clothing which obscure the glabellar area and cannot be removed.
- 19. Subjects do not have known immunization to any botulinum neurotoxin serotype.
- 20. Subjects do not have anticipated need for surgery or overnight hospitalization during the study.
- 21. Subjects do not have history of surgical procedures on forehead and/or periorbital areas or affecting these areas including any lifting procedure (e.g., rhinoplasty, facial lift, suture lift, thread lift, brow lift, eyelid and/or eyebrow surgery).

22. Subjects do not have history of periorbital, mid-facial, or upper-facial treatment with semipermanent or permanent soft tissue fillers (e.g., poly-L-lactic acid, polyalkylimide, polymethylmethacrylate, polytetrafluoroethylene, and silicone), synthetic implantation and/or autologous fat transplantation.

Contraception

- 29. Female subjects that are not pregnant or breastfeeding, and are not considering becoming pregnant or donating eggs during the study or for approximately 30 days after the last dose of study drug or until the end of study, whichever is longer.

Concomitant Medications

abbvie

- 31. Subjects must not have been treated with any investigational drug within 30 days prior to the first dose of study drug or is currently enrolled in another clinical study or was previously enrolled in this study.
- 32. Subjects do not have an anticipated need for treatment with botulinum neurotoxin of any serotype for any reason during the study (other than study drug).

5.3 Contraception Recommendations

Contraception Requirements for Females

Female subjects must follow the following contraceptive guidelines as specified:

• Females, Non-Childbearing Potential

Females do not need to use birth control during or following study drug treatment if considered of non-childbearing potential due to meeting any of the following criteria:

- 1. Premenopausal female with permanent sterility or permanent infertility due to one of the following:
 - Permanent sterility due to a hysterectomy, bilateral salpingectomy, bilateral oophorectomy
 - Non-surgical permanent infertility due to Mullerian agenesis, androgen insensitivity, or gonadal dysgenesis; investigator discretion should be applied to determining study entry for these individuals.

2. Postmenopausal female

- A postmenopausal state is defined as no menses for 12 months without an alternative medical cause.
 - Females on hormone replacement therapy (HRT) and whose menopausal status is in doubt, as determined by the investigator, will be required to use one of the nonhormonal effective contraception methods if they wish to continue their HRT during the study. Otherwise, they must discontinue HRT to allow confirmation of postmenopausal status before study enrollment.

Females, of Childbearing Potential

[figure not shown]
- Review and document pregnancy avoidance recommendations with females of childbearing potential.
- Females of childbearing potential must avoid pregnancy during the study and for at least 30 days after the last dose of study drug or until the end of study, whichever is longer.
- Among the birth control methods given below, females enrolled in sites located in the EU
 must choose from one of the methods 1 through 7 and subjects enrolled in sites located
 outside of EU must choose from one of the methods 1 through 10.

- 1. Combined (estrogen and progestogen containing) hormonal birth control (oral, intravaginal, transdermal, injectable) associated with inhibition of ovulation initiated at least 30 days prior to study Baseline Day 1.
- 2. Progestogen-only hormonal birth control (oral, injectable, implantable) associated with inhibition of ovulation initiated at least 30 days prior to study Baseline Day 1.
- 3. Bilateral tubal occlusion/ligation (can be via hysteroscopy, provided a hysterosalpingogram confirms success of the procedure).
- 4. Intrauterine device (IUD).
- 5. Intrauterine hormone-releasing system.
- 6. Vasectomized partner (provided the partner has received medical confirmation of the surgical success of the vasectomy and is the sole sexual partner of the trial subject).
- 7. Practice true abstinence, defined as: Refraining from heterosexual intercourse when this is in line with the preferred and usual lifestyle of the subject (periodic abstinence [e.g., calendar, ovulation, symptothermal, post-ovulation methods] and withdrawal are not acceptable).
- 8. Male or female condom with or without spermicide.
- 9. Cap, diaphragm, or sponge with spermicide.
- 10. A combination of male condom with cap, diaphragm, or sponge with spermicide (double-barrier method).

Contraception recommendations related to use of concomitant therapies prescribed should be based on the local label.

5.4 Prohibited Medications and Therapy

[figure not shown]

During the study, all other investigational drugs are prohibited.

5.5 Prior and Concomitant Therapy

5.6 Withdrawal of Subjects and Discontinuation of Study

A subject can voluntarily withdraw at any time or will be withdrawn from the study for reasons including, but not limited to, the following:

- Clinically significant abnormal laboratory results or AEs, which rule out continuation of the study drug, as determined by the investigator or the Sponsor. However, when possible, the subject is encouraged to remain in the study for all safety follow-up assessments, even if the subject does not meet retreatment criteria.
- The investigator believes it is in the best interest of the subject.
- The subject requests withdrawal from the study.

- Eligibility criteria violation was noted after the subject started study drug and continuation of the study drug would place the subject at risk.
- Introduction of prohibited medications or dosages and continuation of the study drug would place the subject at risk.
- Subject is significantly noncompliant with study procedures.
- If the subject does not meet the GL severity criterion at Day 43 visit for retreatment, the subject will be followed weekly per the visit schedule (Appendix D) until the FWS grades assessed by both investigator and subject have returned to moderate or severe (investigator and subject grades do not need to match) before being discontinued from the study by completing either the Early Exit or Study Exit Visit.
- If the subject becomes pregnant, then study drug will not be administered, and the subject can either be discontinued from the study after Early Exit Visit procedures are completed or remain in the study for all safety follow-up assessments. If a pregnancy occurs in a study subject, information regarding the pregnancy and the outcome will be collected.
- If the subject declines retreatment despite meeting the retreatment criteria at Day 43 visit, the subject will be discontinued from the study after Early Exit Visit procedures are completed unless the investigator determines the subject should remain in the study for safety follow-up.

For subjects to be considered lost to follow-up, reasonable attempts must be made to obtain information on the subject's final status. At a minimum, 2 telephone calls must be made and 1 certified letter must be sent and documented in the subject's source documentation.

The following events, if applicable, will also cause premature termination of the clinical study:

- Unjustifiable risk and/or toxicity in risk-benefit analysis (decision taken by sponsor representative), e.g., when AEs occur, unknown to date in respect of their nature, severity, duration or frequency in relation to the current established safety profile (substantial changes in risk-benefit considerations), and therefore medical and/or ethical reasons affect the continued performance of the study.
- New scientific evidence becomes available during the study that could affect the patient's safety (benefit-risk analysis no longer positive), e.g., new insights from other clinical trials.
- Request of the sponsor or regulatory agency, e.g., as a consequence of inspection; favorable opinion withdrawn by ethics commission.
- In case of difficulties in the recruitment of the planned number of subjects in the indicated time (insufficient recruitment rate).
- Withdrawal of the license to manufacture or of the permission to import.

AbbVie can terminate this study prematurely, either in its entirety or at any site. The investigator can also stop the study at his/her site if he/she has safety concerns. If AbbVie terminates the study for safety reasons, AbbVie will promptly notify the investigator and appropriate Health Authority.

COVID-19 Pandemic-Related Acceptable Protocol Modification

During the COVID-19 pandemic, it has been necessary to employ mitigation strategies to enable the investigator to ensure subject safety and continuity of care. Acceptable mitigation strategies are identified and included in the Operations Manual (Appendix F), Section 2 and Section 3.

The investigator should contact the sponsor before discontinuing a subject from the study for a reason other than described in the protocol to ensure all acceptable mitigation steps have been explored.

Interruption/Discontinuation of Study Drug Due to COVID-19 Infection

During the study drug dosing period, a subject with confirmed (viral test positive) or suspected COVID-19 infection can only be dosed with study drug if the following COVID-19 viral clearance criteria are met:

 At least 10 days since first positive test result have passed in asymptomatic patients or at least 10 days since recovery, defined as resolution of fever without use of antipyretics and improvement in symptoms.

Delays in study drug dosing due to the above COVID-19 testing guidance for subjects must be discussed with the AbbVie medical contact, along with the possibility of early exit from the study drug dosing period. Follow subsequent protocol Section 5.7 for subjects who discontinued study drug.

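### Section 5.6 takes already-dosed subjects out of the study for an eligibility violation or prohibited medication when withholding the Day 43 injection would be enough

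*Protocol*

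**What the plan says.** The list in Protocol Section 5.6 opens by saying that a subject "will be withdrawn from the study for reasons including, but not limited to, the following". Two of the listed reasons concern the risk of further drug: "Eligibility criteria violation was noted after the subject started study drug and continuation of the study drug would place the subject at risk", and "Introduction of prohibited medications or dosages and continuation of the study drug would place the subject at risk". Neither has a clause on remaining in the study.

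Three other bullets in that list do:
- Adverse event or laboratory abnormality: "when possible, the subject is encouraged to remain in the study for all safety follow-up assessments".
- Pregnancy: drug is withheld and the subject may leave "or remain in the study for all safety follow-up assessments".
- Declined retreatment: the subject is discontinued "unless the investigator determines the subject should remain in the study for safety follow-up".

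Protocol Section 4.1 describes one blinded treatment on Day 1 and adds: "Retreatment is only permitted on the Day 43 visit". Follow-up after that dose runs to Day 84.

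Protocol Section 5.7 has separate rules for subjects not retreated because of line severity (weekly follow-up) or pregnancy (option to stay). One further bullet covers both premature stopping of treatment and premature departure from the study. It prescribes the Early Exit procedures for both, preferably within 2 weeks but not before 30 days after the last treatment. It does not say whether scheduled visits continue for those who only stop treatment.

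SAP Appendix A lists, as a deviation category, a subject who met withdrawal criteria and was kept in.

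**The concern.** Both bullets name continued study drug as the risk, but the remedy they impose is leaving the study. In a trial of one blinded injection and one possible open-label injection, these are easy to separate. Once Day 1 is past, omitting the Day 43 dose avoids all the exposure that withdrawal would avoid. Withdrawal adds only a loss of observation.

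The subjects concerned can be ones whose follow-up matters. Eligibility criterion 10 excludes myasthenia gravis, Lambert-Eaton syndrome and other neuromuscular disease. A subject found after injection to have such a condition could meet the first bullet and be withdrawn, while a subject who becomes pregnant may stay for all safety assessments.

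The loss is mainly scheduled safety assessments. SAP Section 9.2 states its imputation methods for efficacy analyses only, and Protocol Section 7.5 bases antibody percentages on subjects with an interpretable assay at the visit. A missed safety assessment is therefore simply absent. If withdrawal comes before Day 43, later double-blind values on the Facial Wrinkle Scale (FWS) and the questionnaires are also lost. SAP Section 2.1 treats them as missing at random and imputes them.

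**Working it through.** **1. When the two bullets can apply.** Both need a further dose that would be risky. Before Day 43 one dose remains; after the Day 43 visit none does. The bullets can therefore bite only from Day 1 up to and including the Day 43 decision.

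**2. The five bullets side by side (Protocol 5.6).**

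| Reason | Further drug | May the subject stay? |
|---|---|---|
| Adverse event or laboratory result | stopped | yes, encouraged |
| Pregnancy | withheld | yes |
| Declined retreatment | not given | yes, if the investigator so decides |
| Eligibility violation with risk | stopped | nothing stated |
| Prohibited medication with risk | stopped | nothing stated |

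**3. What the minimum follow-up protects.** Day 43 is post-dose day 42, Day 7 is post-dose day 6 and Day 84 is post-dose day 83.
- Withdrawal before Day 43: Protocol Section 6.1 collects adverse events for at least 30 days after the last dose, which covers 30/42 = 71% of the double-blind period. One Early Exit visit follows, no sooner than day 30.
- Decision at Day 43: 42 days have passed since the last dose, so both 30-day minimums are already met. No double-blind value is lost. At stake is scheduled follow-up over the remaining 83 − 42 = 41 days, apart from the Early Exit visit.

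**4. Numbers affected (assumed; the documents give none).** Let f be the fraction of 600 (450 active, 150 placebo; SAP Section 2.4) withdrawn under these bullets before Day 43, with dates spread evenly over 42 days. Then 6/42 = 14.3% fall before Day 7 and 1/42 before Hour 24.

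| f | Withdrawn, 600 × f | Active / placebo | Lose Day 7, × 6/42 | Lose Hour 24, × 1/42 |
|---|---|---|---|---|
| 0.2% | 1.2 | 0.9 / 0.3 | 0.17 | 0.03 |
| 1% | 6 | 4.5 / 1.5 | 0.86 | 0.14 |
| 2% | 12 | 9 / 3 | 1.71 | 0.29 |

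On average a withdrawn subject has 21 of the 42 double-blind days left. How many visits that means is unknown, because the visit schedule is not shown.

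**5. Effect on the Day 7 active response rate.** The gap between imputing the lost active subjects at response rate p and counting them as non-responders is f × 6/42 × p. For p from 50% to 95% (assumed):
- smallest: 0.2% × 0.143 × 0.50 = 0.014 percentage points;
- largest: 2% × 0.143 × 0.95 = 0.27 percentage points.

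This shows how far the choice of missing-data method can move the rate. It is not an estimate of bias against the values that retained subjects would have supplied.

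**6. Power.** SAP Section 2.4 states more than 99% from a two-sided 0.05 chi-square test. The assumed rates are blacked out, so the figure cannot be reproduced exactly. It is plausible at 450:150: placebo 1% with a 10-point difference gives 99.8%, and placebo 5% with a 15-point difference gives 99.9%.

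Stress test: suppose all of f = 2% were lost before Day 7, with lost active subjects counted as failures and lost placebo subjects as responders. The least favourable pair in the assumed range (active 30–95%, placebo 1–5%) is 30% against 5%.
- Active: 0.98 × 0.30 = 0.294. Placebo: 0.98 × 0.05 + 0.02 = 0.069. Difference 0.225.
- Pooled rate (450 × 0.294 + 150 × 0.069)/600 = 0.238; standard error under the null 0.0401; 1.96 × 0.0401 = 0.0787.
- Standard error under the alternative √(0.294 × 0.706/450 + 0.069 × 0.931/150) = 0.0298.
- z = (0.225 − 0.0787)/0.0298 = 4.9, so power stays above 99.9%.

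**The case against.** The strongest reply concerns timing. Nothing is being continued between Day 1 and Day 43, so the natural moment to judge the risk of further drug is the retreatment decision itself. On that reading no double-blind value is lost, and SAP Section 9.1 treats open-label efficacy measures descriptively. This largely stands: double-blind loss is possible because the text does not fix the timing, but it should not lead the argument.

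Second, Section 5.7 is not a blanket exit. It has its own rules for line severity and pregnancy, its silence on scheduled visits does not forbid them, and an early withdrawal still brings a visit at 30 days or later. That stands too. A reader might infer that everyone who stops treatment is removed, or that safety follow-up ends at withdrawal; the documents support neither. The shared bullet still sits awkwardly with the encouragement in 5.6 for adverse event cases to remain.

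Third, relevant text is not available: the Activity Schedule content, the Operations Manual, the full retreatment criteria, Section 5.2 and the substance of Sections 5.4 and 5.5. Any of these might allow such subjects to stay or narrow the trigger. This limits confidence.

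Investigator discretion is not a full answer. Under SAP Appendix A, a site that sensibly keeps such a subject may be recorded as deviating. The Section 5.6 request to consult the sponsor before discontinuing concerns only reasons the protocol does not describe, and these two are described.

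**Conclusion.** The point holds as a minor one, with medium confidence. As shown, two bullets in Section 5.6 require study withdrawal where withholding a single injection would suffice, and three parallel bullets take the less costly route. Section 5.7 does not correct this.

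The main loss is scheduled safety follow-up beyond the Early Exit visit and the 30-day adverse event window. Later double-blind FWS and questionnaire values are lost only if withdrawal precedes Day 43. The number affected is unknown and probably very small; 1.2 to 12 subjects rests wholly on the assumed 0.2% to 2%.

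A reader might infer a threat to the primary result. The documents do not support that. Day 7 values are lost only if withdrawal comes within 6 days of dosing, non-responder and as-observed sensitivity analyses of the primary endpoints are planned (SAP Sections 9.2 and 9.3.3), and power stays above 99.9% under the stress test.

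**What to change.** - **Protocol 5.6**, eligibility-violation and prohibited-medication bullets: add that no further study drug is given and that the subject is encouraged to remain for all scheduled visits and assessments unless consent is withdrawn.
- **Protocol 5.7**: state that subjects who only stop study drug stay on the visit schedule, and that Early Exit is for those who leave the study.
- **Reporting**: use the AGN-151586/None and Placebo/None groups already defined in Protocol Section 7.2 and SAP Section 4.0.
- **SAP Appendix A**: make a matching word change so that a subject kept in without further drug is not counted as a failure to withdraw.

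The cost is a clause in each of two bullets, a sentence and a phrase. No new visits, procedures or analysis groups are needed. A few subjects with violations would complete visits already scheduled. Which events bar a further injection remains a clinical decision, and subjects keep the right to withdraw.
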